5.3.5.5 Persistent or Recurrent Adverse Events

A persistent adverse event is one that extends continuously, without resolution, between participant evaluation timepoints. Such events should only be recorded once on the adverse event eCRF. The initial severity (intensity or grade) of the event will be recorded at the time the event is first reported. If a persistent adverse event becomes more severe, the most extreme severity should also be recorded on the adverse event eCRF. If the event becomes serious, it should be reported to the Sponsor immediately (i.e., no more than 24 hours after learning that the event became serious; see Section 5.4.2 for reporting instructions). The adverse event eCRF should be updated by changing the event from "non-serious" to "serious," providing the date that the event became serious, and completing all data fields related to serious adverse events.

A recurrent adverse event is one that resolves between participant evaluation timepoints and subsequently recurs. Each recurrence of an adverse event should be recorded as a separate event on the adverse event eCRF.

5.3.5.6 Abnormal Laboratory Values

Not every laboratory abnormality qualifies as an adverse event. A laboratory test result must be reported as an adverse event if it meets any of the following criteria:

- Is accompanied by clinical symptoms
- Results in a change in study treatment (e.g., dosage modification, treatment interruption, or treatment discontinuation)
- Results in a medical intervention (e.g., potassium supplementation for hypokalemia) or a change in concomitant therapy
- Is clinically significant in the investigator's judgment

It is the investigator's responsibility to review all laboratory findings. Medical and scientific judgment should be exercised in deciding whether an isolated laboratory abnormality should be classified as an adverse event.

If a clinically significant laboratory abnormality is a sign of a disease or syndrome (e.g., alkaline phosphatase and bilirubin 5× upper limit of normal [ULN] associated with cholestasis), only the diagnosis (i.e., cholestasis) should be recorded on the adverse event eCRF.

If a clinically significant laboratory abnormality is not a sign of a disease or syndrome, the abnormality itself should be recorded on the adverse event eCRF, along with a descriptor indicating whether the test result is above or below the normal range (e.g., "elevated potassium," as opposed to "abnormal potassium"). If the laboratory abnormality can be characterized by a precise clinical term per standard definitions, the clinical term should be recorded as the adverse event. For example, an elevated serum potassium level of 7.0 mEq/L should be recorded as "hyperkalemia".

Observations of the same clinically significant laboratory abnormality from visit to visit should only be recorded once on the adverse event eCRF (see Section 5.3.5.5 for details on recording persistent adverse events).

5.3.5.7 Abnormal Vital Sign Values

Not every vital sign abnormality qualifies as an adverse event. A vital sign result must be reported as an adverse event if it meets any of the following criteria:

- Is accompanied by clinical symptoms
- Results in a change in study treatment (e.g., dosage modification, treatment interruption, or treatment discontinuation)
- Results in a medical intervention or a change in concomitant therapy
- Is clinically significant in the investigator's judgment

It is the investigator's responsibility to review all vital sign findings. Medical and scientific judgment should be exercised in deciding whether an isolated vital sign abnormality should be classified as an adverse event.

If a clinically significant vital sign abnormality is a sign of a disease or syndrome (e.g., high BP), only the diagnosis (i.e., hypertension) should be recorded on the adverse event eCRF.

Observations of the same clinically significant vital sign abnormality from visit to visit should only be recorded once on the adverse event eCRF (see Section 5.3.5.5 for details on recording persistent adverse events).

5.3.5.8 Abnormal Liver Function Tests

The finding of an elevated ALT or AST ($> 3 \times \text{ULN}$) in combination with either an elevated total bilirubin ($> 2 \times \text{ULN}$) or clinical jaundice in the absence of cholestasis or other causes of hyperbilirubinemia is considered to be an indicator of severe liver injury (as defined by Hay's Law). Therefore, investigators must report as an adverse event the occurrence of either of the following:

- Treatment-emergent ALT or AST $> 3 \times \text{ULN}$ in combination with total bilirubin $> 2 \times \text{ULN}$
- Treatment-emergent ALT or AST $> 3 \times \text{ULN}$ in combination with clinical jaundice

The most appropriate diagnosis or (if a diagnosis cannot be established) the abnormal laboratory values should be recorded on the adverse event eCRF (see Section 5.3.5.6) and reported to the Sponsor immediately (i.e., no more than 24 hours after learning of the event), either as a serious adverse event or an adverse event of special interest (see Section 5.4.2).

5.3.5.9 Deaths

All deaths that occur during the protocol-specified adverse event reporting period (see Section 5.3.1), regardless of relationship to study drug, must be recorded on the adverse event eCRF and immediately reported to the Sponsor (see Section 5.4.2). This includes death attributed to progression of AD.

Death should be considered an outcome and not a distinct event. The event or condition that caused or contributed to the fatal outcome should be recorded as the single medical concept on the adverse event eCRF. Generally, only one such event should be reported. If the cause of death is unknown and cannot be ascertained at the time of reporting, **"unexplained death"** should be recorded on the adverse event eCRF. If the cause of death later becomes available (e.g., after autopsy), "unexplained death" should be replaced by the established cause of death. The term **"sudden death"** should not be used unless combined with the presumed cause of death (e.g., "sudden cardiac death").

If the death is attributed solely to progression of AD, "Alzheimer's disease progression" should be recorded on the adverse event eCRF.

Deaths that occur after the adverse event reporting period should be reported as described in Section 5.6.

5.3.5.10 Preexisting Medical Conditions

A preexisting medical condition is one that is present at the Day 1 visit for this study. Adverse events, resolved or ongoing, reported in the OLEs of Studies WN25203 and WN28745 should be considered as medical history in this study. Such conditions should be recorded on the General Medical History and Baseline Conditions eCRF.

A preexisting medical condition should be recorded as an adverse event only if the frequency, severity, or character of the condition worsens during the study. When recording such events on the adverse event eCRF, it is important to convey the concept that the preexisting condition has changed by including applicable descriptors (e.g., "more frequent headaches").

5.3.5.11 Lack of Efficacy or Worsening of Alzheimer's Disease

Events that are clearly consistent with the expected pattern of progression of the underlying disease should not be recorded as adverse event. If there is any uncertainty as to whether an event is due to disease progression, it should be reported as an adverse event.

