4.5.9 Brain Magnetic Resonance Imaging

The MRI should be performed using 1.5-T or 3.0-T scanners, and the same scanner is strongly preferred for an individual participant for the full duration of the study. Only scanners approved for use in the study should be used. MRI will be conducted at baseline for safety monitoring prior to dosing and for structural brain volumes measures. Magnetic resonance imaging will be used during the study to help assess safety such as the occurrence of microbleeds or signs potentially indicative of inflammation or ARIA-E. Additional unscheduled MRI scans may be utilized to better understand relevant CNS related-adverse events (such as increased confusion) or to follow a sign that emerges at a scheduled scan; contrast agent may be used in such a case of follow-up if administration of contrast agent is considered safe for the participant according to local standards.

MRI scans will include the following sequences:

- 3D T₁-weighted gradient recalled echo (GRE) scans
- T₂*-weighted GRE scans
- T₂-weighted fluid-attenuated inversion recovery (FLAIR) scans

The MRI will take approximately 30 minutes to complete.

The MRI scans will be reviewed by a central MRI core laboratory, which will perform the diagnostic reads and assessment of MRI outcome measures. Magnetic resonance imaging scans should preferably be transferred to the central MRI core laboratory electronically. Data transfer from individual study sites to the central MRI core laboratory may take up to 7–10 days, if not done electronically. Upon receipt of the MRI scans from the study sites, the central MRI core laboratory will provide the diagnostic reads. MRI results must be made available to investigators prior to *the next dosing visit*.

The MRI facility qualification and scan quality control will be performed by the central MRI core laboratory.

The MRI scan performed for the follow-up visit in Studies WN25203 and WN28745 will be used as baseline scan in this study, where possible. In case there might be a gap between follow-up visit from OLEs of WN25203/WN28745 and the first dose in this study of more than six months MRI has to be repeated.

Additional instructions regarding the procedures for MRI facility qualification and MRI scan acquisition and transmittal to the central reading facility can be found in the MRI Manual.

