5.2.1 Adverse Events

According to the ICH guideline for GCP, an adverse event is any untoward medical occurrence in a clinical investigation subject administered a pharmaceutical product, regardless of causal attribution. An adverse event can therefore be any of the following:

- Any unfavorable and unintended sign (including an abnormal laboratory finding), symptom, or disease temporally associated with the use of a medicinal product, whether or not considered related to the medicinal product

- Any new disease or exacerbation of an existing disease (a worsening in the character, frequency, or severity of a known condition), except as described in Section [5.3.5.11](#)
- Recurrence of an intermittent medical condition (e.g., headache) not present at baseline
- Any deterioration in a laboratory value or other clinical test (e.g., ECG, X-ray) that is associated with symptoms or leads to a change in study treatment or concomitant treatment or discontinuation from study drug
- Adverse events that are related to a protocol-mandated intervention, including those that occur prior to assignment of study treatment

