5.3.5.1 Amyloid-related Imaging Abnormality Findings

Not every ARIA finding in MRI qualifies as an adverse event. An ARIA finding must be reported as an adverse event if it meets any of the following criteria:

- ARIA-E which is symptomatic (i.e., accompanied by CNS symptoms), and/or
- ARIA that results in a change in study treatment (e.g., dosage modification, treatment interruption, or treatment discontinuation), and/or
- Is otherwise clinically significant in the investigator's judgment

Any accompanying symptoms should also be captured as separate adverse events.

It is the investigator's responsibility to review all ARIA findings.

Observations of the same clinically significant ARIA finding should only be recorded once on the adverse event eCRF (see Section 5.3.5.5 for details on recording persistent adverse events).

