- b Informed consent should be obtained by the participants before any study procedures are performed, and may be obtained while they are active in the qualifying study; however, enrollment in this study is contingent upon completion of the qualifying study, and any premature discontinuation of study participation or study drug in the qualifying study, or failure to meet any other eligibility criterion (see Section [4.1.1](#)), precludes enrollment in this study.
- c MRI results should be available before dosing on Day 1. At subsequent visits indicated in the schedule, MRI scans must be performed within 20 days after dose administration and results made available and reviewed before the next scheduled dose. Participants will be asked if they experience CNS adverse events up to one week before each MRI is performed.
- d Includes volumetric outcome measures.
- e Vital signs include HR, BP, and *temperature*. The same arm should be used for all blood pressure measurements. HR and BP should not be measured unless 15 minutes have passed since the last blood draw. Weight will be recorded yearly at the time of physical examination.
- f Perform after the participant has been in a supine position for 5 minutes. ECGs for each participant should be obtained at baseline and any time during the study if deemed necessary by the investigator from the same machine whenever possible and performed prior to any blood draws, brain MRI scans.

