Appendix 2 Management Rules for Amyloid-Related Imaging Abnormalities (continued)

ARIA-E = amyloid-related imaging abnormality–edema/effusion; ARIA-H = amyloid-related imaging abnormality–hemosiderin deposition; BGTS = Barkhof grand total score; CNS = central nervous system; LH = leptomeningeal hemosiderosis; MRI = magnetic resonance imaging; Q4W = every 4 weeks.

Notes:

- Symptomatic ARIA-E is defined as onset or worsening of CNS symptom(s) that is/are temporally associated with ARIA-E MRI findings.
- In exceptional cases of (1) an ARIA-E that is asymptomatic with BGTS <4 and considered stable over consecutive MRI images by the Sponsor and investigator; or (2) symptomatic ARIA-E for which the imaging evidence of ARIA-E has resolved but the CNS symptoms continue, gantenerumab can be either reintroduced or up-titrated, as applicable, and Q4W MRI monitoring may no longer be necessary, as determined by the Sponsor and investigator.
- Investigators may choose to perform additional MRI monitoring for ARIA at any time.
- In this study, "up-titration to target dose" applies to participants who may have started with lower dose level due to the length of dosing gap and their ARIA-E history (see [Appendix 3](#)) and need to return to the dose that they were receiving in the qualifying study (e.g., 1200 mg or 900 mg Q4W).

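### Symptomatic ARIA-E may be under-ascertained: the pre-MRI question asks about CNS adverse events, the definition rests on CNS symptoms, and no step reopens earlier progression attributions

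*Combined protocol and SAP*

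**What the plan says.** **Definition.** The notes to Appendix 2 read: "Symptomatic ARIA-E is defined as onset or worsening of CNS symptom(s) that is/are temporally associated with ARIA-E MRI findings". The definition turns on symptoms and timing. It does not mention whether the symptom was recorded as an adverse event (AE), and it gives no time window.

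**Scan-linked question.** Footnote c of the Schedule of Activities, repeated in footnote l for the follow-up or early termination scan, says: "Participants will be asked if they experience CNS adverse events up to one week before each MRI is performed".

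**Progression rule.** Section 5.2.1 counts exacerbation of an existing disease as an AE, except as set out in Section 5.3.5.11. That section says: "Events that are clearly consistent with the expected pattern of progression of the underlying disease should not be recorded as adverse event". Its next sentence adds: "If there is any uncertainty as to whether an event is due to disease progression, it should be reported as an adverse event".

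**ARIA reporting rule.** Section 5.3.5.1 makes ARIA-E with CNS symptoms reportable as an AE and adds: "Any accompanying symptoms should also be captured as separate adverse events". Section 5.2.4 says that data on associated symptoms will be collected for ARIA-E and ARIA-H.

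**General AE elicitation.** Sections 5.3.1 and 5.3.2 have AEs sought at each contact, with open questions about new or changed health problems.

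**The concern.** The participants have Alzheimer's disease, so cognitive or behavioural decline always has a ready explanation. The same decline can be a symptom of ARIA-E. Section 4.5.9 uses increased confusion as its example of a CNS-related AE that may lead to an unscheduled scan, and confusion is also a plausible feature of progression. If decline is judged to be clear progression before a scan, it is not an AE, and a question about CNS adverse events need not bring it up.

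Two things depend on the label. First, for ARIA-E with a Barkhof grand total score (BGTS) below 4, it decides which row of Appendix 2 applies. No view is taken here on the actions in those rows. Second, it shapes how ARIA-E is described in an open-label, single-arm study whose main objective is safety. Loss of symptoms by this route moves cases in one direction only, from symptomatic to asymptomatic.

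**Working it through.** The point is about wording, so the main check is to follow one case through the text.

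1. A participant becomes more confused between scans. By the Schedule of Activities, MRI falls at Weeks 24, 52, 76, 104, 128, 156, 180 and 208, so scheduled scans are 24 or 28 weeks apart.
2. The investigator applies Section 5.3.5.11. If any doubt is felt, the worsening is an AE and the later steps work. If it is judged clearly consistent with progression, it is not recorded as an AE.
3. Around the next scan, the participant is asked about CNS adverse events. Read literally, the worsening in step 2 is outside the question.
4. The scan shows ARIA-E with BGTS of at least 1 and below 4. Appendix 2 now needs a symptomatic or asymptomatic label. Its definition would take in the confusion if it is temporally associated. The investigator must recall it, because neither the AE record nor the footnote question supplies it.
5. No text triggers a second look. Section 5.3.5.3 has a retrospective correction rule, but it replaces AEs that were previously reported; this worsening was not. Section 5.2.4 promises symptom data but describes no re-review.
6. If the case is labelled asymptomatic and the participant is on target dose, Appendix 2 brings no treatment change. Under Section 5.3.5.1 the ARIA-E then need not be an AE unless judged otherwise clinically significant. The symptom and the ARIA-E could both be missing from the AE record.
7. The MRI finding itself survives. Scans are read centrally (Section 4.5.9), and Section 6.5 summarises ARIA-E and ARIA-H findings in their own right.

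**Scale.** The plan gives no figure for misclassification, so there is none to reproduce. Two numbers give context.

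- One relabelled participant in Part 1 (n = 116, Section 6.1): 1/116 = 0.86 percentage points.
- ARIA-E cases that might need a label: new ARIA-E in the open-label extensions (Section 1.2.2) was 47 of 154 in WN25203 and 71 of 219 in WN28745. Pooled, (47 + 71)/(154 + 219) = 118/373 = 31.6%, and 0.316 × 116 = 36.7. This is best read as a ceiling. The extensions included titration to higher doses (Section 1.2.1.4), whereas most participants here continue at their last dose, and Section 5.1.1.1 says the risk may fall with time.

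The missing input is the share of ARIA-E cases with concurrent worsening already attributed to progression. The documents give nothing from which to estimate it, so the calculation stops there.

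**The case against.** The strongest reply is that the plan already forbids the error. A reader might infer that its wording allows symptomatic ARIA-E to be filed as asymptomatic. It does not. The Appendix 2 definition and Section 5.3.5.1 apply whether or not the symptom was first recorded as an AE, and the investigator must review all ARIA findings. Filing such a case as asymptomatic would breach the plan. This stands, and it limits the point to ascertainment.

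A reader might also infer that any CNS worsening resembling progression is left out of the AE record. That drops the word 'clearly' and the uncertainty sentence. That sentence carries no time limit, so a new ARIA-E finding could itself be taken as a source of uncertainty about an earlier judgment. That reading is reasonable, but nothing prompts anyone to apply it after the scan.

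The footnote question is also not the only source. AEs are sought at every visit with open wording, the MMSE is scheduled at the same visits as the MRI, and Section 4.5.9 treats increased confusion as an AE worth investigating. These help. However, answers to the open questions still pass through Section 5.3.5.11 before they become AEs, and an MMSE score does not settle whether a change accompanied ARIA-E.

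Finally, the symptomatic share is not a named endpoint: Section 6.5 lists incidence, nature, severity and timing. That is correct and lowers the stakes for the analysis. The label still selects the Appendix 2 row. It is also true that worsening many weeks before a scan may not be temporally associated at all, and with no window defined the documents cannot settle that.

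**Conclusion.** The concern holds as a gap in ascertainment. The scan-linked question and the definition it should serve use different terms, Section 5.3.5.11 can place a relevant symptom in the space between them, and no step reopens that judgment when ARIA-E appears. The existing safeguards reduce the risk but do not remove it.

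Overall ARIA-E incidence on MRI is unaffected. The number of participants who might change label cannot be derived; multiplying the 36.7 above by an assumed misattribution rate would give a figure with no support in the documents. All that can be said is that each relabelled participant is 0.86 percentage points of 116.

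The conclusion assumes that sites use footnotes c and l as written, and that eCRF pages or training not included in these documents do not already ask about symptoms regardless of attribution. It deserves correction because the change is small and affects what is asked around every MRI.

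**What to change.** 1. In footnotes c and l of the Schedule of Activities, replace *CNS adverse events* with *new or worsened CNS symptoms, whether or not attributed to AD progression*. This brings the question into line with the Appendix 2 definition.
2. Reconcile Section 5.3.5.11 with Section 5.3.5.1 and Appendix 2 by adding that, when ARIA-E is found, the investigator reconsiders earlier attributions to progression under the existing any-uncertainty rule.

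The second change deliberately stops short of requiring all temporally associated worsening to be recorded as an AE. Decline is expected in this population and the term has no window, so an automatic rule would go too far.

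The cost is two wording changes and a short review of notes for each ARIA-E finding. The downside is that some true progression will be counted as ARIA-E symptoms, making the safety description slightly less favourable. No dosing or management rule is proposed or altered.

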5.3.5.12 Hospitalization or Prolonged Hospitalization

Any adverse event that results in hospitalization (i.e., inpatient admission to a hospital) or prolonged hospitalization should be documented and reported as a serious adverse event (per the definition of serious adverse event in Section 5.2.2).

An event that leads to hospitalization under the following circumstances should not be reported as an adverse event or a serious adverse event:

- Hospitalization for respite care
- Planned hospitalization required by the protocol (e.g., for study drug administration or insertion of access device for study drug administration)
- Hospitalization for a preexisting condition, provided that all of the following criteria are met:
 - The hospitalization was planned prior to the study or was scheduled during the study when elective surgery became necessary because of the expected normal progression of the disease
 - The participant has not experienced an adverse event

